## 6.2 Evaluation and Follow-up

6.2.1 Timing of Assessments: all subjects will be evaluated prior to initiation of treatment, weekly during the course of the primary protocol study treatment period and for eight weeks following the completion of proton beam radiation therapy, and 90 days following the start of radiation therapy by the treating radiation oncologist. Patients will be evaluated every three months during the first year following radiation therapy, approximately every six months during the second year following therapy, and annually for years three to five following therapy. Effort will be made to follow subjects beyond five years to assess for toxicity related to radiation treatment and survival, either by the treating radiation oncologist or a referring physician.

6.2.2 Pre-treatment: after determining eligibility, pre-treatment patient assessment will include history and physical examination, performance status assessment (Appendix C), toxicity assessment (as

per protocol section 6.2.5), and quality of life assessment with EORTC QLQ-C30 (Appendix D), Testicular Cancer Patient Diary Card (Appendix E), and EuroQol EQ-5D (Appendix F). Patients will also undergo pre-treatment laboratory evaluation to include complete blood count, semen analysis, follicle-stimulating hormone level, luteinizing hormone level, testosterone, and serum creatinine or creatinine clearance. **Patients who object to the semen analysis or are not covered by their insurance company to have the analysis will not be excluded from the study. If the semen analysis is performed, an optional DNA fragmentation will also be performed from the semen analysis if covered by the patients insurance. This portion of the analysis will only be performed at the Coordinating Center, University of Pennsylvania, and not at participating sites.**

#### 6.2.3

6.2.4 During Radiation Therapy: each patient will be assessed at least weekly during radiation therapy treatment. Each assessment will include a pertinent physical examination, performance status assessment (Appendix C), toxicity assessment (as per protocol section 6.2.5), laboratory evaluation to include complete blood count (optional), and quality of life assessment with EORTC QLQ-C30 (Appendix D), Testicular Cancer Patient Diary Card (Appendix E), and EuroQol EQ-5D (Appendix F).

6.2.5 Immediately Following Radiation Therapy: each patient will be assessed weekly for the first eight weeks following the completion of radiation therapy. Each assessment will include quality of life assessment with EORTC QLQ-C30 (Appendix D), Testicular Cancer Patient Diary Card (Appendix E), and EuroQol EQ-5D (Appendix F). At the discretion of the treating radiation oncologist, these weekly assessments may be performed in the physician clinic, via Internet-based surveys, via questionnaires from the patient home, or over the phone.

6.2.6 Toxicity Assessment: Patients will be treated and followed for a minimum of 90 days after the start of radiation treatment to determine safety (acute toxicity). The Common Toxicity Criteria v4.0 (Appendix A) [73] will be used to report acute adverse events that occur within 90 days of treatment initiation and late adverse events that occur after 90 days of protocol therapy initiation for up to 5 years.

6.2.7 Years 1-5 Post Treatment: each patient will be assessed 90 days following the start of radiation therapy and then every three months for one year, every six months during the second year following therapy, and annual for years three to five or longer following therapy. Each follow-up assessment will include an interval history and physical examination, performance status assessment (Appendix C), toxicity assessment (as per protocol section 6.2.5), quality of life assessment with EORTC QLQ-C30 (Appendix D) and EuroQol EQ-5D (Appendix F), and laboratory evaluation with serum creatinine and/or creatinine clearance, complete blood count, testosterone (at specified timepoints), lactate dehydrogenase, human chorionic gonadotropin, and alpha-fetoprotein. Additionally, semen analysis will be obtained 12 months following the completion of therapy. A chest x-ray or CT Chest will be obtained at each patient follow-up visit during years one through five following the completion of therapy. In patients with continued follow-up beyond five years, chest x-rays or CT Chest thereafter will be performed at the discretion of the evaluating physician. For patients not receiving pelvic radiation therapy, follow-up assessments will include a CT abd/pelvis or MRI abd/pelvis scan annually for the first three years following the completion of therapy.

- Toxicity assessment from years five through 15 will include inquires of any renal disease, cardiac disease, and second malignancies that the study participants may have been diagnosed with since the completion of the primary protocol study treatment period. If a patient has been

diagnosed with a second malignancy, details of the disease primary location, histology, staging, treatment regimen received, and disease status should be obtained. Copies of pertinent pathology reports, imaging reports, and treatment details should also be obtained.

## 7 Statistical Plan

This is a study of proton therapy for patients with stage I, IIA, and IIB testicular seminoma. Feasibility (i.e., *logistics* of proton planning, dosimetry, scheduling and deliver) was established prior to this trial, based on 9 patients treated at PENN with proton therapy to the study region of interest for seminoma or other malignancies. All 9 patients met the feasibility criteria, as documented by the Director of Clinical Research, [name], PhD. Thus, the feasibility endpoint has been sufficiently established and this trial will not include early termination for feasibility logistics of protons.

### 7.1 Phase II Study

#### 7.1.1 Design and Objectives.

- In patients receiving adjuvant radiation therapy in MRC TE19, 30% reported moderate to severe lethargy at 3 weeks from starting treatment as compared to 8% in those treated with single-dose carboplatin. At 3 to 4 weeks (approximately day 25), 24% of radiation-treated and 7% of carboplatin-treated patients reported moderate to severe lethargy. We will monitor the rate of moderate to severe lethargy **at 3 weeks**, as reported on the patient symptom diary card.
- Because proton therapy is expected to spare normal tissues, the rate of moderate to severe lethargy should be less than experienced with photon therapy. It is desirable for proton radiation to yield a reduced rate of lethargy similar to single-dose carboplatin. Our hypothesis is that the 3-week lethargy rate will be less than <35%, which approximates the rate observed with photon therapy. This hypothesis holds for patients with Stage I, IIA, or IIB seminoma. The study is powered to detect a reduction in the lethargy rate to 20%. A single stage phase II design will be followed.

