Despite reductions in radiation doses and treatment fields, surveillance has emerged as an alternative and increasingly utilized adjuvant course. Approximately 15% to 20% of unselected patients with stage I seminoma who undergo surveillance following orchiectomy develop disease recurrence (35-43). As greater than 80% of these relapses occur in the para-aortic lymph nodes, deferring immediate adjuvant therapy and administering chemotherapy or radiation therapy upon relapse allows for successful salvage therapy in most patients, with equivalent overall survival rates as for patients receiving immediate adjuvant therapy (41-43). However, treatment of patients undergoing surveillance who relapse is usually more intensive and associated with increased morbidity (44-45). More recently, groups have advocated a risk-adapted management strategy to guide adjuvant therapy (46). As the risk of relapse is higher in patients with tumor sizes great than 4 cm, rete testis invasion, or pT3 or pT4 disease, in the absence of a contraindication to adjuvant therapy, only patients with pT1 or pT2 histologies and smaller tumors who are committed to long-term follow-up are ideal candidates for surveillance (8, 33, 43, 46).

Short-course adjuvant carboplatin for one or two cycles has emerged as an alternative to adjuvant radiation therapy or surveillance (8, 47-48). An MRC and European Organization for Research and Treatment of Cancer trial (MRC/EORTC ISRCTN27163214) randomized 1,447 patients with pT1 to pT3 stage I seminoma to one course of carboplatin or adjuvant radiotherapy to 20 Gy to 30 Gy in 200 cGy daily fractions primarily to the para-aortic region (16-17). At a median follow-up of 6.5 yrs, there was no difference in 5-year relapse-free survival rates between the carboplatin arm and the radiation therapy arm (94.7% vs. 95.5%, HR 1.25, 90% CI 0.83 to 1.89). Patients in the carboplatin arm had higher rates of Grade 1 or Grade 2 thrombocytopenia (12% vs. 2%,  $p<0.0001$ ) and Grade 3 or Grade 4 thrombocytopenia (4% vs. 0%,  $p<0.0001$ ), whereas patients in the radiation therapy arm had higher rates of dyspepsia (17% vs. 8%,  $p<0.0001$ ) and a trend towards increased lethargy and time off of work in the acute setting. Additionally, fewer new contralateral testicular germ cell cancers were observed in the carboplatin arm (0.2% vs. 1.2%, HR 0.22,  $p=0.03$ ).

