## 3 Subject Selection and Withdrawal

### **3.1 Accrual**

This study plans to enroll 56 evaluable patients over 72 months. The University of Pennsylvania, Penn satellites, Walter Reed National Military Medical Center, other affiliated Department of Defense (DOD) hospitals, and Massachusetts General Hospital (MGH), see in excess of 20 patients with stage I, IIA, and IIB testicular seminoma per year. Of the patients with seminoma treated annually at these participating institutions, we would reasonably expect to accrue 8 to 10 patients on study annually. Only MGH and the University of Pennsylvania will be treating patients with protons. The Walter Reed National Military Medical Center/Department of Defense affiliates will be referring patients to the University of Pennsylvania.

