#### 7.1.4 Statistical Analyses.

- Acute and Late Toxicity: All acute and late toxicities will be graded by CTC Version 4.0 and tabulated. Toxicity rates and 95% confidence intervals will be calculated.
- Analysis by Radiation Therapy Type: all subjects enrolled in this study will be followed and assessed for all endpoint analyses. However, a separate analysis may be performed for subjects who were treated with photon therapy as a portion of their planned course of radiation therapy.
- Moderate to Severe Lethargy: The 3-week rate and 95% CI will be computed. A one-sample one-sided chi-square test will be performed to test the null hypothesis that the lethargy rate is 35% (same as photon) versus the alternative hypothesis that the rate is reduced to 20%. Patients must have a minimum of 21 days of follow-up to be included. As a secondary analysis, the 3-week lethargy rate and 95% exact CI will be computed for each disease stage. A Fisher's exact test will be employed compare these rates, to determine whether lethargy rates significantly differ by disease stage.
- Clinical Efficacy: Time to local failure and time to distant failure will be estimated by the cumulative incidence method within a competing risks framework (competing risks are local failure, distant failure, death). Relapse-free survival, cause-specific survival, and overall survival will be estimated by the Kaplan-Meier method. Median values and 95% confidence intervals will be calculated.
- Quality of Life: Longitudinal quality of life measurements will be examined by plots of mean $\pm$  SD over time. Repeated measures ANOVA or linear mixed effects models (to assess the impact of fixed effects covariates), will be used to analyze the repeated observations. Piecewise linear models may be required to fit non-linear trends, as expected for the initial decline and then gradual increase in quality of life measures.

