## 7.2 Sample Size/Power and Trial Duration

A maximum of 59 patients may be enrolled, in order to accrue 56 evaluable patients, assuming that the attrition rate (i.e., missing patient symptom diary at 3 weeks) will be at most 5%. With 56 evaluable patients, there will be 80% power for a chi-square test at one-sided 5% type I error, to test the null hypothesis that the rate of moderate to severe lethargy at 3 weeks is  $\geq 35\%$  versus the alternative hypothesis that the rate is  $\leq 20\%$ . To complete accrual for the phase II portion of the trial, the entire trial should be active for six years.

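### The primary null of 35% is labelled as the photon rate, but the only 3-week photon rate in the protocol is 30%; rejecting 35% does not by itself show less lethargy than with photons

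*Combined protocol and SAP*

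**What the plan says.** Section 7.1.1 sets the primary endpoint as moderate to severe lethargy at 3 weeks, taken from the patient diary card. It gives the reference figures from the randomised trial of radiotherapy against carboplatin: "30% reported moderate to severe lethargy at 3 weeks from starting treatment as compared to 8% in those treated with single-dose carboplatin". It adds 24% for radiotherapy at about day 25. The following bullet states the hypothesis: "Our hypothesis is that the 3-week lethargy rate will be less than <35%, which approximates the rate observed with photon therapy". It then extends it to every stage enrolled: "This hypothesis holds for patients with Stage I, IIA, or IIB seminoma".

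Section 7.1.4 makes the link to photons firmer. The one-sided test is of the "null hypothesis that the lethargy rate is 35% (same as photon"), against a reduction to 20%. Section 7.2 sizes the trial on the same pair of rates, testing "the null hypothesis that the rate of moderate to severe lethargy at 3 weeks is" at least 35% against at most 20%, with 56 evaluable patients, one-sided 5% error and 80% power.

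Section 1.1 describes the source trial as having randomised "1,447 patients with pT1 to pT3 stage I seminoma to one course of carboplatin or adjuvant radiotherapy", so the 30% is a stage I figure.

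**The concern.** The plan gives two different numbers for one quantity. The photon rate at the endpoint's own time point is 30%; the null described as the photon rate is 35%. The other photon lethargy rates in the document are lower still: 24% at about day 25 (7.1.1), and 20% and 5% four weeks after 30 Gy and 20 Gy respectively (1.1). The null is therefore above every photon figure that the plan cites.

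This is the only powered test in the trial. The 5% error rate protects a comparison with 35% and nothing lower, yet under the plan's wording a rejection would be read as an improvement over photons. The planned difference is 15 points from 35%, but only 10 points from 30%. One third of the effect that the trial is sized for is thus the unexplained gap between 35% and 30%.

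**Working it through.** **Inputs.** Null 35% and alternative 20% (7.1.4, 7.2); one-sided 5% error, 80% power, 56 evaluable patients (7.2); cited 3-week photon rate 30% (7.1.1); accrual of 8 to 10 patients a year (3.1).

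**1. The plan's sample size.** For a one-sample test of a proportion,

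n = [(z₀.₉₅·√(p₀(1−p₀)) + z₀.₈₀·√(p₁(1−p₁))) / (p₀−p₁)]²

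- p₀ = 0.35, p₁ = 0.20: [(0.7845 + 0.3366)/0.15]² = 55.87, so 56. The plan's figure reproduces.
- p₀ = 0.30, p₁ = 0.20: [(0.7538 + 0.3366)/0.10]² = 118.9, so 119.

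**2. Rejection rule at n = 56.** z = (x − 56·0.35)/√(56·0.35·0.65). At x = 13, z = −1.849 (reject); at x = 14, z = −1.569 (do not reject). The rule is at most 13/56, or 23.2%.

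**3. Exact probability of rejecting, P(X ≤ 13), X binomial with n = 56.**

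| True rate | P(reject 35%) |
|---|---|
| 35% | 4.1% |
| 34% | 5.6% |
| 33% | 7.6% |
| 32% | 10.0% |
| 31% | 13.1% |
| 30% | 16.8% |
| 20% | 78.3% |

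The probability equals 5% at a true rate of 34.4%. The 5% protection is therefore already lost for any photon reference below about 34.4%.

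**4. What the boundary result shows.** At 13/56 the exact two-sided 95% CI is 13.0% to 36.4%. Exact one-sided 95% upper bounds:

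| Events | Upper bound |
|---|---|
| 10/56 | 28.4% |
| 11/56 | 30.4% |
| 12/56 | 32.4% |
| 13/56 | 34.4% |

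Results of 11, 12 or 13 of 56 reject 35% without putting the exact bound below 30%. At a true rate of 20% these results occur with probability 78.3% − 42.0% = 36.3%, so this is not a remote case.

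**5. Testing 30% directly at n = 56.**

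| Rule | Exact size at 30% | Power at 20% | Power at 15% |
|---|---|---|---|
| ≤10/56 (exact) | 2.9% | 42.0% | 78.9% |
| ≤11/56 (chi-square, z = −1.69) | 5.7% | 55.3% | 87.5% |

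**6. Could stage mix give 35%?** The plan states no stage split, so the shares here are assumptions. With stage I at 30% and stage I share s, a blended 35% needs a stage II photon rate of (0.35 − 0.30s)/(1 − s).

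| Stage II share | Stage II photon rate needed |
|---|---|
| 10% | 80% |
| 20% | 55% |
| 30% | 47% |
| 50% | 40% |

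**The case against.** A sponsor may choose its own benchmark in a single-arm phase II trial. The formal primary objective in section 2.2 asks only whether the rate is at most 35% and does not name photons. Section 7.1.1 says only that 35% approximates the photon rate, and no section sets out a formal superiority claim over photons. This is fair: 35% as a bare benchmark is not the fault, and the sample-size arithmetic is right. What remains is the label in 7.1.4, which the plan's own 30% contradicts.

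The 30% may also be too low a reference here. The source trial treated stage I patients, mainly to the para-aortic region, in 200 cGy fractions. This protocol allows smaller fractions over up to four weeks, optional pelvic fields in stage I, and a mandatory pelvic field with a boost in stage II. Section 1.1 reports more lethargy at 30 Gy than at 20 Gy. The 30% also carries sampling error. A somewhat higher reference is therefore plausible, and the blended-rate table, which fixes stage I at 30%, may make 35% look harder to reach than it is. But the plan makes no such argument and applies 35% to stage I as well.

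Not every rejection is affected. By the plan's own chi-square test, 11/56 or fewer also rejects 30%, so on that test only 12 or 13 of 56 are at issue; at a true 30% they have probability 16.8% − 5.7% = 11.1%. The 16.8% is still the correct chance of rejecting 35% at a true rate of 30%, and the ≤11/56 rule itself exceeds 5%.

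Finally, 7.1.4 already plans a 95% CI for the primary rate, and for the stages "the 3-week lethargy rate and 95% exact CI will be computed for each disease stage". A careful reader could set these beside 30%, but the plan never calls for that comparison and tells the reader that 35% is the photon rate.

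**Conclusion.** The concern holds. The label on the only powered test disagrees with the plan's own reference figure, and 35% has no stated source. If the proton rate equals the cited 3-week photon rate, the trial rejects its photon-labelled null about 17% of the time, not 5%. This rests on taking the cited 30% as a fixed reference for the enrolled population; for references of 31% to 34% the figure runs from 13.1% down to 5.6%. A rejection can still support a claim against 30% when the count is low enough: at most 10/56 by the exact bound. This should be fixed, but it is a matter of justification and interpretation and does not invalidate the test of 35%.

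**What to change.** Either give a source and calculation for 35% at the planned stage mix, or remove the clause in 7.1.1 and the parenthesis in 7.1.4 that equate 35% with the photon rate. Add to 7.1.4:

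> Rejecting 35% does not by itself show less lethargy than with photons. The exact one-sided 95% upper confidence bound will be compared with the cited 3-week photon rate of 30%. A rate below the cited photon rate will be claimed only if the bound is below 30% (at most 10 of 56; the count will be recomputed if the evaluable number differs).

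The exact bound is preferred for this claim because the chi-square rule of ≤11/56 has an exact size of 5.7%.

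The cost is wording only: no extra patients, and the primary test of 35% is unchanged. The downside is that the photon claim needs ≤10/56 rather than ≤13/56, and at a true rate of 20% it succeeds 42% of the time.

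An alternative is to move the null to 30% at n = 56 and restate size and power from step 5 of the working. Power near 80% then requires a target of about 15%, which the documents do not support and the sponsor would have to justify.

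Keeping 80% power for 30% versus 20% would take about 119 evaluable patients. Section 3.1 says "we would reasonably expect to accrue 8 to 10 patients on study annually", so that is 119/10 = 11.9 to 119/8 = 14.9 years, and it is not proposed.

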#### 7.1.2 Endpoints

- Acute Toxicity is defined as any Grade 3 or higher non-hematologic toxicity that occurs within 90 days following the start of proton therapy. NCI Common toxicity criteria (CTC Version 4.0) grades will be employed (Appendix A).
- Late Toxicity is defined as any Grade 3 or higher non-hematologic toxicity that occurs beyond 90 days following the start of proton therapy. NCI Common toxicity criteria (CTC Version 4.0) grades will be employed (Appendix A).
- Clinical Efficacy: Time to local failure will be defined as the time from the start of radiation therapy to local failure. Time to distant failure will be defined as the time from the start of radiation therapy to distant failure. Relapse-free survival will be defined from the time from the start of radiation therapy to any failure or death. Cause-specific survival will be defined from the time from the start of radiation therapy to death due to seminoma. Overall survival will be

defined from the time from the start of radiation therapy to death due to any cause or last patient follow-up. These outcomes will be summarized at the end of the phase II study.

- Quality of Life Measures: EORTC QLQ-C30, Testicular Cancer Patient Diary Card, and EuroQol EQ-5D will be evaluated at multiple times during and post-radiation. We hypothesize that compared to baseline, quality of life measures will worsen during and immediately post-radiation and will then gradually improve after radiation. These deficits are expected to be less than those seen for photon treated patients and the time course to return to baseline should be shortened. These outcomes will be summarized at the end of the phase II study.
- Moderate to Severe Lethargy will be scored on the Testicular Cancer Patient Diary Card (Appendix E). The rate of moderate to severe lethargy at week 3 will be evaluated. This outcome will be summarized at the end of the phase II study.

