Despite these promising early findings, carboplatin is associated with an uncertain frequency of late relapses and a need for more rigorous CT surveillance with abdominal and pelvic CT imaging at every visit for up to 10 years (8, 33-34, 49). The radiation exposure from this more frequent CT surveillance may result in an increase in secondary malignancies (50-52). Carboplatin also has potential risks of acute nephrotoxicity, ototoxicity, neurotoxicity, and gonadal damage, as well as long-term cardiac disease and secondary malignancies (15, 19). Population-based cancer registry studies of patients primarily treated with combination chemotherapy reveal an increased risk of secondary solid malignancies highest among patients receiving both chemotherapy and radiotherapy (RR=2.9, 95% CI=1.9-4.2), with similar risks for patients treated with adjuvant radiation therapy alone (RR=2.0, 95% CI = 1.9-2.2) or adjuvant chemotherapy alone (RR=1.8, 95% CI = 1.3-2.5) (19). Several studies have also reported increased risks of secondary leukemias and myelodysplastic syndrome following chemotherapy for testicular cancer (22, 53-60).

Proton beam radiation therapy is a way of delivering radiation that has the potential of minimizing both acute and late toxicities associated with standard photon radiation therapy. We propose to use beam proton radiation therapy to deliver 20.0 Gy (RBE) to 30.0 Gy (RBE) to the para-aortic lymph node region, with or without 20.0 Gy (RBE) to 30.0 Gy (RBE) to the ipsilateral pelvic nodal region, for the adjuvant treatment of patients with stage I testicular seminoma. Thus, we are examining in this study the ability of proton beam radiation therapy to reduce the risk of acute and late toxicities in this group of patients.

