### **3.6 Early Withdrawal of Subjects**

- 3.6.1 Progressive Disease: Subjects who have clinical or radiologic evidence of progressive disease will undergo an evaluation to document the nature of the abnormality. If progressive cancer is diagnosed and further treatment planned, subjects will be considered off study and all efforts will be made to follow the patients for survival and toxicity data.
- 3.6.2 Principal Investigator Decision: Subjects may be withdrawn at any time during the study if the Principal Investigator believes it is in the subject's best interest to be withdrawn. In this event, the reasons for withdrawal will be documented.
- 3.6.3 Subject Participation: Refusal to continue treatment, follow-up, or comply with the protocol, or the withdrawal of consent. In this event, the reasons for withdrawal will be documented.
- 3.6.4 New information becomes available that warrants discontinuation of the protocol.

Once the subject is withdrawn from the study, the primary reason for withdrawing from the study must be clearly documented in the subject's records and on the CRF. The investigator will assess each subject for response at the time of withdrawal.

Every effort will be made to follow subjects off study for toxicity and survival. Survival will be followed for a minimum of five years by means of medical records and an annual phone call by a member of the research team to the subject if no medical records are available. Every effort will be made to follow patients for overall survival.

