### 5.2 Chemotherapy as Salvage Therapy

If a patient is found to have clinical or radiographic evidence of disease recurrence or a worrisome radiographic abnormality, pathological assessment is strongly encouraged, but not required, to confirm disease recurrence. The pathological confirmation of disease recurrence at any site or the initiation of salvage therapy will be considered a failure of protocol treatment, and such patients will be removed from study and followed for late effects and survival. Subsequent management and salvage therapy of patients who have failed protocol treatment will be left to the discretion of the treating oncologist, with the treatment modality and treatment regimen dictated by the location and extent of tumor recurrence at the time of evaluation.

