## **8.4 Reporting of Serious Adverse Events**

Adverse Event Reporting Period: the study period during which Adverse Events must be collected and Serious Adverse Events must be reported is normally defined as the period from the initiation of any study procedures to the end of the study treatment follow-up (off study at progression). This protocol will begin assessment of AEs and SAEs following the first treatment fraction of radiation therapy. Therefore, only treatment emergent events will be evaluated.

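### Late toxicity has no attribution test and no separation at salvage treatment, and Sections 3.6.1 and 5.2 conflict with 8.4 on whether events after relapse are collected

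*Combined protocol and SAP*

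**What the plan says.** Section 7.1.2 defines the endpoint by grade, type and time only: "Late Toxicity is defined as any Grade 3 or higher non-hematologic toxicity that occurs beyond 90 days following the start of proton therapy". Section 8.2.2 refers back to 7.1.2 for what counts as an acute or late radiation effect. Section 6.2.6 sets the reporting window: "late adverse events that occur after 90 days of protocol therapy initiation for up to 5 years". For the analysis, Section 7.1.4 states: "All acute and late toxicities will be graded by CTC Version 4.0 and tabulated". It adds rates with 95% confidence intervals, but no rule on attribution, relapse or salvage.

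Three sections deal with patients who relapse:

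- Section 3.6.1, on progression with further treatment planned: "subjects will be considered off study and all efforts will be made to follow the patients for survival and toxicity data".
- Section 5.2, on confirmed recurrence or the start of salvage: "such patients will be removed from study and followed for late effects and survival".
- Section 8.4 has the usual adverse event period run "to the end of the study treatment follow-up (off study at progression". It then moves the start of that period to the first fraction and leaves the end unchanged.

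Objective 2.3.3 is to assess late complications of proton irradiation to the para-aortic and pelvic regions.

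**The concern.** The objective asks what proton irradiation does. The endpoint counts whatever happens after day 90, provided it is Grade 3 or higher and non-hematologic. A patient who relapses and receives chemotherapy or further radiation can then have a qualifying event caused by the salvage treatment, and nothing in 7.1.2 or 7.1.4 keeps it out of the proton rate.

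The opposite error is also possible. A site that follows 8.4 stops collecting at progression, so it loses salvage toxicity together with any genuine late proton effect in the same patient. The two treating centers could handle identical patients differently and both be following the protocol.

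Reducing late toxicity is part of the rationale in Sections 1.1 and 1.2. With 56 patients and few late Grade 3 events expected, one misassigned event visibly changes the reported rate.

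**Working it through.** **1. The plan's own figure.** The documents give no target rate or power for late toxicity. The stated size of 56 belongs to the lethargy test in Section 7.2 (35% against 20%, one-sided 5%, 80% power):

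n = [(1.645 × √(0.35 × 0.65) + 0.842 × √(0.20 × 0.80)) / 0.15]² = 55.87, rounded up to 56. Allowing 5% attrition, 56 / 0.95 = 58.9, so 59 enrolled.

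Both figures reproduce, and neither depends on how late toxicity is defined.

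**2. The sections side by side, for an event after salvage.**

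| Section | Collected after relapse? | Counted as late toxicity? |
|---|---|---|
| 3.6.1 | Yes, best effort | Not addressed |
| 5.2 | Yes | Not addressed |
| 7.1.2 with 8.2.2 | Not addressed | Yes, if Grade 3 or higher, non-hematologic, after day 90 |
| 7.1.4 | Not addressed | Yes, all late toxicities tabulated |
| 8.4 | No, the period ends at progression | Would not arise |

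**3. How many patients could be affected.** The documents give only background rates from conventional treatment.

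- Stage I: Section 1.1 gives 95.5% five-year relapse-free survival in the radiotherapy arm of the carboplatin trial, so about 4.5% failing. 56 × 0.045 = 2.5 patients.
- Stage IIA/IIB: Section 1.2 gives five-year disease-free survival of at least 90%, so at most about 10%. 56 × 0.10 = 5.6 patients.
- Mixed cohort, assuming the 80% Stage I share that Section 1.1 quotes for seminoma generally: 56 × (0.8 × 0.045 + 0.2 × 0.10) = 3.1 patients.
- Chance of at least one relapse at 4.5%: 1 − 0.955⁵⁶ = 92%.

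**4. Effect on the rate.** Assume no proton-related late event, and let x salvaged patients have a qualifying event. Exact (Clopper-Pearson) 95% intervals with n = 56:

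| x | Rate | 95% CI |
|---|---|---|
| 0 | 0% | 0-6.4% |
| 1 | 1.8% | 0.05-9.6% |
| 3 | 5.4% | 1.1-14.9% |
| 6 | 10.7% | 4.0-21.9% |

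The documents do not give the proportion of salvaged patients with a Grade 3 or higher non-hematologic event, so x is an assumption. In the mixed cohort, x = 3 already means that almost every salvaged patient has one. x = 6 needs, in addition, a cohort made up entirely of Stage II patients relapsing at the maximum rate.

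**The case against.** The strongest reply is that the documents tie late toxicity to radiation in several places. Section 8.2 is about radiation toxicities. Section 6.2.1 speaks of radiation-related toxicity beyond five years. Section 9.1.2 puts toxicity assignments in the Medical Monitor's report. Appendix A lists treatment-related secondary malignancy. A sensible investigator might not call salvage toxicity a proton effect. That is fair as a prediction, but none of this wording enters the endpoint definition or the analysis, and 8.2.2 sends the reader back to the unqualified definition in 7.1.2.

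It can also be said that counting every event whatever the later therapy is a conservative safety summary, and that cutting off at salvage discards real proton effects that emerge late. This stands. It is a reason to show both rates rather than replace one with the other. Plain censoring would also have no meaning for the simple proportion planned in 7.1.4.

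Some stronger readings are tempting, but the documents do not support them:

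- A reader might take the sentence in 7.1.4 that "all subjects enrolled in this study will be followed and assessed for all endpoint analyses" as settling that events after salvage count. It stands in the item on radiation therapy type, and the sentence after it concerns patients treated partly with photons. It does not address salvage.
- A reader might think that all severe chemotherapy toxicity enters the rate. The definition excludes hematologic events, and the Grade 3-4 carboplatin finding reported in Section 1.1 is thrombocytopenia.
- A reader might use the second-cancer risk in Section 1.1, "highest among patients receiving both chemotherapy and radiotherapy (RR=2.9, 95% CI=1.9-4.2", against 2.0 (1.9-2.2) for radiotherapy alone, to size the problem. The intervals overlap, the figures come from registry cohorts, and Section 1.1 places the radiotherapy excess at 10 to 35 years, whereas 6.2.6 reports late events up to 5 years.

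**Conclusion.** The point holds as a gap in the definition combined with a contradiction between sections. It would go too far to say that the plan reports salvage toxicity as proton toxicity: under 7.1.2 and 7.1.4 such events would be counted, and under 8.4 they would not be collected. The fault is that the answer depends on the section a site follows, and either outcome distorts the quantity named in Objective 2.3.3.

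The size is modest. About 3 of 56 patients might be salvaged, with a range of 2.5 to 5.6. One salvage-related event raises the upper confidence limit from 6.4% to 9.6%, and a shift to 5.4% (1.1-14.9%) is close to the most that is plausible. This rests on background relapse rates applying to protons, on no proton-related late event, and on an assumed number of salvaged patients with an event.

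Late toxicity is secondary and descriptive. The early termination rule in 7.1.3 uses acute toxicity only, so no trial decision is affected.

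**What to change.** 1. Make 8.4 agree with 3.6.1 and 5.2 on whether late events are collected after relapse, and for how long.
2. Record the start date and modality of the first salvage treatment on the CRF.
3. In 7.1.4, report the proton late-toxicity rate from events before the first salvage treatment. If it is estimated over time, use cumulative incidence with salvage start and death as competing events.
4. Beside it, show the rate from all events under the present 7.1.2 definition, and a separate table of post-salvage events by modality.

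This takes a few sentences in 7.1.4 and 8.4, two data fields and one extra table, and it needs no additional patients. The cost is slightly less follow-up in the pre-salvage rate. A genuine proton effect that appears after salvage will be visible only in the all-events rate and the separate table, which is why all three should be reported.
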